5.5.2 Sponsor Follow-Up

For serious adverse events, adverse events of special interest, and pregnancies, the Sponsor or a designee may follow up by telephone, fax, electronic mail, and/or a monitoring visit to obtain additional case details and outcome information (e.g., from hospital discharge summaries, consultant reports, autopsy reports) in order to perform an independent medical assessment of the reported case.

5.6 ADVERSE EVENTS THAT OCCUR AFTER THE ADVERSE EVENT REPORTING PERIOD

After the end of the adverse event reporting period (defined as 90 days after the last dose of study drug), all deaths, regardless of cause, should be reported through use of the Long-Term Survival Follow-Up eCRF. In addition, if the investigator becomes aware of a serious adverse event that is believed to be related to prior study drug treatment, the event should be reported through use of the Adverse Event eCRF.

5.7 EXPEDITED REPORTING TO HEALTH AUTHORITIES, INVESTIGATORS, INSTITUTIONAL REVIEW BOARDS, AND ETHICS COMMITTEES

The Sponsor will promptly evaluate all serious adverse events and adverse events of special interest against cumulative product experience to identify and expeditiously communicate possible new safety findings to investigators, IRBs, ECs, and applicable health authorities based on applicable legislation.

To determine reporting requirements for single adverse event cases, the Sponsor will assess the expectedness of these events using the following reference documents:

- Cobimetinib Investigator's Brochure
- Atezolizumab Investigator's Brochure

The Sponsor will compare the severity of each event and the cumulative event frequency reported for the study with the severity and frequency reported in the applicable reference document.

Reporting requirements will also be based on the investigator's assessment of causality and seriousness, with allowance for upgrading by the Sponsor as needed.

6. STATISTICAL CONSIDERATIONS AND ANALYSIS PLAN

This study evaluates the preliminary efficacy, safety, and pharmacokinetics of atezolizumab plus cobimetinib in patients with *BRAF*^{V600} WT metastatic or unresectable locally advanced melanoma who have progressed on prior anti-PD-1 therapy (Cohorts A and B), and atezolizumab monotherapy in patients with *BRAF*^{V600} WT metastatic or unresectable locally advanced melanoma who have not been previously treated (Cohort C).

The primary analysis will be conducted *in Cohorts A and B approximately 24 weeks after the last patient is enrolled in Cohort A. At this time, Cohorts A and B will have a minimum follow up of approximately 24 weeks. The primary analysis for Cohort C may be analyzed independently, with a minimum of 24 weeks follow up for patients in Cohort C.* Both separate and pooled efficacy and safety analyses will be performed on Cohorts A and B, given their similar patient populations. Additional tumor immunology and biomarker analyses will also be conducted on Cohort B. Study data will be described and summarized for Cohort C separately.

6.1 DETERMINATION OF SAMPLE SIZE

This study is designed for hypothesis generation with the intention to provide an informative evaluation on the selected efficacy endpoints. No formal inferential testing is planned. Approximately 152 patients are anticipated to be enrolled, with *approximately 90 patients in Cohort A, 12 patients in Cohort B, and 50 patients in Cohort C.*

A combined 102 patients in Cohorts A and B allows for a robust comparison against historical control of ipilimumab and chemotherapy in patients who have previously progressed on anti-PD1 therapy, which generally have response rates of less than 17%. For example, with 102 patients in Cohorts A and B, observing 26 patients with objective response corresponds to ORR (95% CI) of 25.5% (17.4%, 35.1%) and observing 60 patients with disease control corresponds to a DCR (95% CI) of 58.8% (48.6%, 68.52%).

Enrolling 50 patients in Cohort C provides reasonably reliable estimates of the ORR and DCR in patients who have not been previously treated to allow for an accurate understanding of the achievable magnitude of efficacy in this population.

For example, observing 17 patients with objective response corresponds to ORR (95% CI) of 34.0% (21.1%, 48.8%) and observing 32 patients with disease control corresponds to DCR (95% CI) of 64% (49.2%, 77.1%). Enrolling 50 patients in Cohort C also provides an opportunity to explore the preliminary efficacy in relevant patient subgroups including biomarker subgroups defined by PD-L1 expression.

6.2 SUMMARIES OF CONDUCT OF STUDY

Enrollment, eligibility violations, and patient disposition will be summarized. Study treatment administration will be summarized for all treated patients.

6.3 SUMMARIES OF DEMOGRAPHIC AND BASELINE CHARACTERISTICS

Demographic variables and other baseline and disease characteristics will be summarized using descriptive statistics.

6.4 EFFICACY ANALYSES

Efficacy analyses will include all patients who receive at least one dose of study drug.

6.4.1 Primary Efficacy Endpoint

ORR is defined as the proportion of patients whose objective response is a CR or a PR. Objective response is defined as a CR or PR on two consecutive occasions ≥ 4 weeks apart, as determined by the investigators using RECIST v1.1. A 95% Clopper-Pearson CI will be calculated for the ORR.

DCR is defined as the proportion of patients with a CR, PR, or SD at 16 weeks after the baseline tumor assessment.

6.4.2 Secondary Efficacy Endpoints

For patients who achieve an objective response, DOR is defined as the time from the first occurrence of a documented objective response to disease progression, as determined by the investigator according to RECIST v1.1, or death from any cause, whichever occurs first. Data for patients who have not experienced disease progression or have not died will be censored at the last tumor assessment date. Data for patients with no post-baseline tumor assessment will be censored at 1 day after the first treatment date. Kaplan-Meier methodology will be used to estimate the median PFS, and the 95% CI of the median DOR arm will be constructed using the Brookmeyer and Crowley method (Brookmeyer and Crowley 1982).

PFS is defined as the time from Cycle 1, Day 1 to the first occurrence of disease progression, as determined by the investigator according to RECIST v1.1, or death from

any cause, whichever occurs first. The censoring and analysis method for PFS will be the same as that for DOR.

For Cohort C, ORR, DCR, DOR, and PFS will also be determined by the IRC according to RECIST v1.1 using the same methods as described above.

OS is defined as the time from Cycle 1, Day 1 to death from any cause. For patients who are alive at the time of analysis data cutoff, OS time will be censored at the date the patient was last known to be alive. Survival time for patients with no post-baseline survival information will be censored at 1 day after the first treatment date. OS will be analyzed in a manner similar to PFS.

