aPD-1 = anti-programmed cell death 1; ECOG = Eastern Cooperative Oncology Group; PD = progressive disease; PS = performance score; RECIST = Response Evaluation Criteria in Solid Tumors.

Figure 5 Treatment and Biopsy Schedule (Cohort A)

[figure not shown]
D = day; IV = intravenous; PO = by mouth.

Figure 6 Treatment and Biopsy Schedule (Cohort B)

D= day; IV= intravenous; PO= by mouth.

Figure 7 Treatment and Biopsy Schedule (Cohort C)

D= day; IV= intravenous.

After signing informed consent, eligible patients will undergo screening procedures that include testing for the *BRAF*^{V600} mutation; laboratory tests; 12-lead ECGs; left ventricular function evaluation (LVEF; echocardiogram [ECHO] or multiple-gated acquisition [MUGA] scan); contrast-enhanced brain computed tomography (CT) scan or magnetic resonance imaging (MRI); contrast-enhanced CT or MRI scan of the chest, abdomen, and pelvis; and ophthalmologic (for Cohorts A and B) and dermatologic assessments.

All patients will be closely monitored for safety and tolerability throughout the study. The National Cancer Institute Common Terminology Criteria for Adverse Events, Version 4.0 (NCI CTCAE v4.0) will be used to characterize the toxicity profile of the study treatments for all patients. The protocol includes a detailed risk management plan for monitoring and managing molecule-specific and potential combination toxicities (see Section 5).

For all cohorts, tumor response will be evaluated by the investigator according to RECIST v1.1 (see Appendix 3); immune-modified RECIST v1.1 (see Appendix 4) will also be assessed by the investigator. For Cohort C, tumor response will also be determined by the independent review committee (IRC) according to RECIST v1.1. All measurable and non-measurable lesions will be documented at screening. Response will be assessed at 8-week intervals until investigator-determined disease progression (according to RECIST v1.1), death, or initiation of subsequent anti-cancer therapy, whichever occurs first. Patients who experience disease progression must have scans repeated 4 weeks after initial documentation of progression to confirm disease progression. Tumor assessments are to continue according to schedule in patients who discontinue treatment for reasons other than confirmed disease progression, unless subsequent anti-cancer therapy is initiated.

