6.4.3 Exploratory Efficacy Endpoints

ORR, DOR, and PFS as determined by the investigator according to immune-modified RECIST (see [Appendix 4](#)) will be analyzed using the same methods as described above.

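### IRC and immune-modified PFS/DOR reuse last-scan censoring although scanning follows investigator RECIST v1.1 progression, so these estimates can be biased upward; a sensitivity analysis and consistent scan-stop wording are needed

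*Combined protocol and SAP*

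**What the plan says.** Section 6.4.2 gives one censoring rule for investigator-assessed DOR and PFS: "Data for patients who have not experienced disease progression or have not died will be censored at the last tumor assessment date". Progression is one event and death is the other ("or death from any cause, whichever occurs first"). For Cohort C, where the IRC endpoints are secondary, "DOR, and PFS will also be determined by the IRC according to RECIST v1.1 using the same methods as described above". Section 6.4.3 treats "ORR, DOR, and PFS as determined by the investigator according to immune-modified RECIST" in the same way: they "will be analyzed using the same methods as described above". These are exploratory and cover all cohorts.

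The scan schedule follows a different criterion. Section 3.1 states: "Response will be assessed at 8-week intervals until investigator-determined disease progression (according to RECIST v1.1), death, or initiation of subsequent anti-cancer therapy". It then adds: "Patients who experience disease progression must have scans repeated 4 weeks after initial documentation of progression to confirm disease progression". Section 4.4.5 ends scans at investigator progression that has been confirmed 4 weeks later, or at death. Appendix 1 (footnote l for each cohort) continues scans to loss of clinical benefit in patients treated beyond progression, which Section 3.1.2 permits in all cohorts on listed conditions.

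No section gives a rule or sensitivity analysis for patients who have progressed by the investigator's v1.1 reading but not by the criterion being analysed.

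**The concern.** Kaplan-Meier estimation assumes that a censored patient has the same future risk as those still under observation. A patient whose scans have ended because the investigator called progression is unlikely to meet that assumption. If the IRC did not call progression on the available scans, the IRC analysis censors this patient at the last one, and any IRC progression that follows is never seen.

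The same can happen under immune-modified RECIST, where disagreement with v1.1 is built in. Appendix 4 does not treat a new lesion alone, or worsening of non-target lesions, as progression; Appendix 3 treats both as progression.

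The study plans no formal testing, so the descriptive estimates are its product. If IRC or immune-modified PFS came out longer than investigator v1.1 PFS, the plan as written could not separate a real difference from a censoring artefact.

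**Working it through.** **No planned figure to reproduce.** The documents state no expected IRC or immune-modified PFS or DOR, no event count and no discordance rate.

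**What the rules do to a patient with investigator v1.1 progression at scan time t**

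1. Progression by the second criterion at t: event at t.
2. Progression by the second criterion on the 4-week repeat scan or a later scan: event at that scan.
3. Neither, and the patient dies before cutoff: event at death, possibly later than an unseen progression.
4. Neither, and the patient is alive at cutoff: censored at the last scan. This is the informative group.

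**Size, for IRC PFS only**

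From the documents: scans every 8 weeks; repeat scan at 4 weeks; minimum follow-up 24 weeks (Section 6); 5.5-month median PFS from Study PCD4989g (Section 1.3.2.1, a mixed population); deaths as events. Assumed: about 12 months of accrual; the share of investigator progressions not called by the IRC at that scan (discordance); the further delay to IRC progression; survival after investigator progression; and, in a variant, 40% of patients scanned 16 weeks beyond progression.

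Overstatement = (12-month Kaplan-Meier PFS under the planned rule) − (the same if scans continued to IRC progression). Median shifts in months are multiplied by 52/12 to give weeks.

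| Discordance; median delay; median survival after progression | Scans continue | Planned rule | Overstatement | With 40% scanned further | Median shift, planned rule |
|---|---|---|---|---|---|
| 10%; 4 mo; 18 mo | 27.4% | 27.4% | 0.0 | +0.1 | 0 |
| 30%; 2 mo; 12 mo | 28.9% | 31.2% | +2.3 | +1.3 | 0 |
| 40%; 2 mo; 12 mo | 30.5% | 33.4% | +2.9 | +1.7 | (8.574 − 7.365) × 52/12 = 5.2 wk |
| 40%; 2 mo; 18 mo | 30.9% | 34.7% | +3.8 | +2.1 | (9.206 − 7.365) × 52/12 = 8.0 wk |

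Three harsher settings, with 12-month median survival after progression:

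| Discordance; mean delay | Overstatement | With 40% scanned further | If no patient died after progression |
|---|---|---|---|
| 25%; 8 wk | +2.6 | +1.5 | +4.1 |
| 35%; 16 wk | +3.0 | +1.7 | +5.4 |
| 50%; 16 wk | +4.9 | +2.6 | +9.1 |

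The last column shows why deaths matter. It does not describe this plan, which counts them.

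A check run with the same inputs (follow-up uniform over 24 to 76 weeks, 400,000 patients) for 50% discordance and an 8-week mean delay gave +5.6 points and a 5.8-week median shift at 12-month survival after progression. At 18-month survival it gave +6.7 points and 8 weeks. The upper end therefore depends on survival after progression.

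**Does scanning beyond progression remove the problem?** Only if those scanned are typical. With 30% discordance, 2-month median delay and 12-month survival, a separate run gave a reference of 28.6% and a planned estimate of 31.0%. Scanning a random 40% for 16 weeks more gave 30.1%; scanning the 40% who progress most slowly gave 31.0%, no gain. Section 3.1.2 restricts continued dosing to patients who are clinically stable with evidence of benefit, so selection is plausible.

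**Counting investigator progression as the event.** In the same setting this gives 24.7%, an error of 24.7 − 28.6 = −3.9 points against 31.0 − 28.6 = +2.4 for the planned rule. The two estimates bracketed the reference in five of six settings tried; the exception was 10% discordance with a 1-month delay, where the bias was 0 to 0.4 points.

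**The case against.** The strongest reply is that the effect is limited and the endpoints are not primary. Much of this stands.

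- A reader might infer that imaging ends at the first investigator progression. It does not. The 4-week repeat scan is mandatory, Sections 3.1 and 4.4.5 can be read as keeping unconfirmed progressions on schedule, and Appendix 1 continues scans for patients treated beyond progression.
- A reader might infer that all discordant patients are censored and that both sets of endpoints are overstated as a matter of fact. Those with later IRC progression on a scan, and those who die before cutoff, are events. The bias is upward or near zero, and its size rests on quantities the documents do not give.
- For immune-modified RECIST, measurable new lesions enter the tumour-burden sum, so some v1.1 new-lesion progressions will also be immune-modified progressions. No magnitude was computed for these endpoints.
- A reader might infer that the IRC endpoints were added to check open-label readings, or that scans after progression are withheld from the IRC. The amendment summary gives no purpose, and IRC reading procedures are not described.
- The plan estimates medians and no 12-month landmark, and the median shift is zero in several settings. With 50 patients the sampling standard deviation of a 12-month estimate is about 9 points, larger than the bias.
- Counting investigator progression as the event is often further from the truth than the planned estimate and moves the IRC result towards the investigator's. It cannot replace the planned analysis.

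What remains is that the censoring is tied to a different criterion from the one analysed, the bias does not shrink with sample size, and the plan offers no means of seeing it.

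**Conclusion.** The concern holds in a limited form. Sections 6.4.2 and 6.4.3 carry last-scan censoring over to endpoints whose follow-up is governed by another criterion, and say nothing about discordant patients. Those who are alive and no longer scanned are censored informatively, so IRC PFS/DOR and immune-modified PFS/DOR can be biased upward.

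For IRC PFS, with 10% to 50% discordance, the repeat scan, deaths as events and 12-month median survival after progression, the overstatement is about 0 to +5 points at 12 months (5.6 in the least favourable check) and 0 to about 6 weeks in the median. It is smaller if many patients are scanned beyond progression, and larger if survival after progression is longer: one full 8-week scan interval in the median in some 18-month settings. Discordance, delay and survival after progression are assumptions. DOR and the immune-modified endpoints share the mechanism but were not quantified. The primary endpoints are unaffected by this point, and only descriptive estimates are at stake.

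**What to change.** Keep the planned analysis and make these changes.

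1. Add to Sections 6.4.2 and 6.4.3 a prespecified sensitivity analysis of IRC and immune-modified PFS and DOR. It counts investigator v1.1 progression as an event at its date when no progression by the analysed criterion is seen before scans stop. Label it a lower bound, to be reported beside the planned estimate and not in place of it.
2. Tabulate how many patients are censored in this way for each endpoint and, for Cohort C, the investigator/IRC concordance on progression.
3. State that scans already taken after investigator progression are included in the IRC read.
4. Reconcile the scan-stop wording. Section 3.1 names first progression and new anti-cancer therapy; Section 4.4.5 requires confirmed progression and does not name new therapy; Appendix 1 uses progression or, for patients treated beyond it, loss of clinical benefit.

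The cost is some protocol and analysis text, two tables and one extra, less favourable estimate per endpoint. No new scans are needed.

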6.4.3 Exploratory Efficacy Endpoints

ORR, DOR, and PFS as determined by the investigator according to immune-modified RECIST (see [Appendix 4](#)) will be analyzed using the same methods as described above.

6.5 SAFETY ANALYSES

The safety analyses will include all patients who receive at least one dose of study drug.

Safety will be assessed through summaries of adverse events, changes in laboratory test results, changes in vital signs, and study treatment exposure.

Verbatim description of adverse events will be summarized by mapped terms and appropriate thesaurus levels and graded according to NCI CTCAE v4.0. All adverse events that occur during or after the first study drug dose will be summarized by NCI CTCAE grade. In addition, serious adverse events, severe adverse events (Grades ≥ 3), adverse events of special interest, and adverse events leading to study drug discontinuation or interruption will be summarized accordingly. Multiple occurrences of the same event will be counted once at the maximum severity. The proportion of patients who experience at least one adverse event will be reported by toxicity term.

Study drug exposure, including treatment duration, number of doses, and dose intensity, will be summarized using descriptive statistics.

All deaths and causes of death will be summarized.

Laboratory data with values outside the normal ranges will be identified. In addition, relevant laboratory data and vital signs will be summarized.

6.6 PHARMACOKINETIC ANALYSES

The PK analyses will include patients who have received at least one dose of study drug and for whom at least one evaluable PK sample (actual dose and actual sampling time recorded for each sample) is collected. Since only a few samples are collected from patients, data will be analyzed using the existing population PK model for post hoc

estimates of apparent clearance or systemic clearance for cobimetinib and atezolizumab respectively. Maximum or minimum concentration (C_{\max} or C_{\min}) will be reported for individual patients and summarized by study day, as data permit. In addition, the relationship between drug exposure (cobimetinib or atezolizumab) and safety and efficacy endpoints will be explored for exposure-response relationship.

Additional PK analyses will be conducted as appropriate on the basis of the available data.

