3.3.8 Rationale for Pharmacokinetic Assessments

The proposed PK sampling scheme for assessment of cobimetinib and atezolizumab concentration, together with available data from other clinical studies, will be used to investigate any potential drug interactions between the two molecules by comparing the PK data from this study with single-agent data from previous studies. In addition, single-agent atezolizumab data from Cohort C will be compared to atezolizumab PK collected in the combination cohorts (Cohort A and Cohort B).

Atezolizumab is primarily eliminated by catabolism to inactive metabolites and, therefore, it has a low potential for drug interactions. Cobimetinib is metabolized primarily by CYP3A, and to a lesser extent by UGT2B7, based on in vitro studies. Because of the differences in metabolism, no drug–drug interaction is anticipated between cobimetinib and atezolizumab.

A sparse sampling strategy will be applied in this study. Samples for pharmacokinetic (PK) characterization of cobimetinib and atezolizumab will be collected as outlined in [Appendix 2](#). The pharmacokinetics of each compound each drug will be compared with single-agent data for each molecule from previous studies or previously developed population PK models.

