Appendix 2 Schedule of Pharmacokinetic, Immunogenicity, and Biomarker Samples

Cohort A

Visit	Timepoint	Sample Type(s)
Cycle 1, Day 1	Prior to the first infusion	Atezolizumab PK and ADA (serum)
	30 (\pm 10) minutes following the end of atezolizumab infusion	Atezolizumab PK (serum)
	2–4 hours after the cobimetinib dose	Cobimetinib PK (plasma)
Cycle 1, Day 15	Prior to cobimetinib dose 2–4 hours post cobimetinib dose	Cobimetinib PK (plasma)
Cycles 2, 3, 4, 8, 12, and 16	Prior to the first infusion	Atezolizumab PK and ADA (serum)
Cycles 1 and 2, Day 1 At time of tumor assessments (preferably within 3 days) At disease progression	Predose	Biomarker (plasma, PBMC)
Treatment discontinuation visit ^a	At visit	Atezolizumab PK and ADA (serum) Biomarker (plasma, PBMC) ^b
120 days \pm 30 days after last atezolizumab infusion	At visit	Atezolizumab PK and ADA (serum)

ADA=anti-drug antibody; PBMC=peripheral blood mononuclear cell; PK=pharmacokinetic.

Note: Except for Day 1 of Cycle 1, all other study visits and assessments during the treatment period should be performed within \pm 3 days of the scheduled date. Study assessments may be delayed or moved ahead of the window to accommodate holidays, vacations, and unforeseen delays.

^a Patients who discontinue study drug will return to the clinic for a treatment discontinuation visit 30 (\pm 3) days after the last dose of study drug. The visit at which response assessment shows progressive disease may be used as the treatment discontinuation visit.

^b At confirmed disease progression, lack of clinical benefit, or at treatment discontinuation.

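### Averaged post hoc cobimetinib clearances may understate a drug interaction; Section 6.6 should estimate the combination effect on CL/F directly

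*Combined protocol and SAP*

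**What the plan says.** Section 3.3.8 gives the purpose of the sparse PK sampling: to "investigate any potential drug interactions between the two molecules by comparing the PK data from this study with single-agent data from previous studies". It also allows earlier population PK models as the reference, adds a comparison of Cohort C with Cohorts A and B for atezolizumab, and expects no interaction because the two drugs are eliminated by different routes.

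Section 6.6 gives the method. Because samples are few, "data will be analyzed using the existing population PK model for post hoc" "estimates of apparent clearance or systemic clearance for cobimetinib and atezolizumab respectively". Any treated patient with at least one evaluable PK sample is included. Cmax or Cmin "will be reported for individual patients and summarized by study day, as data permit". The section closes with "Additional PK analyses will be conducted as appropriate on the basis of the available data". It mentions no combination covariate, no re-estimation of the model, no shrinkage diagnostic and no criterion for an interaction.

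Appendix 2 sets the cobimetinib sampling. Cohort A has one sample on Cycle 1 Day 1, "2–4 hours after the cobimetinib dose", and two on Day 15 (predose and 2–4 h post dose). Cohort B has only the Day 15 pair, and Section 4.2.2.2 puts its first atezolizumab dose on that same day.

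Table 1 lists concentrations at specified timepoints as the PK endpoints. Section 6.1 plans no formal testing.

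**The concern.** A post hoc (empirical Bayes) clearance is a compromise between a patient's own samples and the model's typical value, and the fewer the informative samples, the closer it stays to the typical value. If that value represents cobimetinib alone, it is also the no-interaction value. The pull then has the same direction in every patient, so it neither averages out nor shrinks as the cohort grows.

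The inclusion rule adds to this. A Cohort A patient with only the Day 1 sample returns close to the model's typical clearance and would enter the average as apparent evidence of no change.

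No test is planned, so readers will interpret the estimated ratio itself, and the protocol already expects no interaction. A fall in cobimetinib clearance means higher exposure to the drug that Section 5.1.1 links to serous retinopathy, left ventricular dysfunction and CPK elevation. Understating it would be an error in the unsafe direction.

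**Working it through.** **Plan's own figure.** There is none. The documents give no PK variability, residual error, shrinkage, interaction margin or PK sample size.

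**Inputs from the documents.** Cobimetinib samples per patient: 3 in Cohort A, 2 in Cohort B (Appendix 2). Cohort A size: about 90 (Section 6.1).

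**Assumed inputs.** Between-patient SD of log CL/F (ω) 0.30–0.60; residual SD on the log scale (s) 0.20–0.50; between-patient SD of log V/F 0.40; half-life 24 or 48 h; ka 0.8/h; model typical value equal to the single-agent value; true clearance ratio 0.70, which is an exposure increase of 1/0.70 − 1 = 43%.

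**Step 1: simple shrinkage.** With n equally informative samples, the retained share of a log shift is w = ω²/(ω² + s²/n), and a true ratio of 0.70 is reported as 0.70^w.

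| ω | s | n | w | 0.70 reported as |
|---|---|---|---|---|
| 0.60 | 0.20 | 3 | 0.36/(0.36 + 0.0133) = 0.96 | 0.71 |
| 0.45 | 0.35 | 3 | 0.2025/(0.2025 + 0.0408) = 0.83 | 0.74 |
| 0.30 | 0.50 | 3 | 0.09/(0.09 + 0.0833) = 0.52 | 0.83 |
| 0.30 | 0.50 | 2 | 0.09/(0.09 + 0.125) = 0.42 | 0.86 |

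**Step 2: how informative each sample is.** In a one-compartment oral model, when clearance falls by 30%:
- The Cycle 1 Day 1 concentration at 3 h changes by a factor of only 1.01–1.02. Cohort A therefore has in effect two samples that inform clearance.
- The Day 15 predose concentration rises 1.46–1.58 fold. This observed quantity is not shrunk.
- Cohort B's Day 15 predose sample precedes any atezolizumab, and its second sample is taken on the day of the first infusion. Cohort B says almost nothing about an effect of atezolizumab on cobimetinib.

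**Step 3: linearised post hoc estimate at the planned times** (3 h, Day 15 predose, Day 15 at 3 h). Across all 18 combinations of half-life, ω and s, the retained share is 0.42–0.96 in both cohorts, so 0.70 is reported as 0.71–0.86.

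**Step 4: nonlinear check,** 300 simulated Cohort A patients per setting.

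| ω, s, half-life | Post hoc ratio | Share retained | Eta-shrinkage |
|---|---|---|---|
| 0.60, 0.20, 24 h | 0.73 | 90% | 7% |
| 0.45, 0.35, 48 h | 0.78 | 71% | 21% |
| 0.30, 0.50, 48 h | 0.89 | 33% | 38% |

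The share retained is relative to the nominal 0.70. Each row is one simulated sample, so it carries some sampling noise.

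**Step 5: estimating the effect instead.** A separate simulation used 90 patients, 100 trials per scenario, half-life 44 h, CL variability 30–50%, residual error 20–40%, and 0–15% of patients missing Day 15. Mean post hoc ratios were 0.732–0.859. On the log scale that retains ln 0.732/ln 0.70 = 87% down to ln 0.859/ln 0.70 = 43%. Maximum marginal likelihood on the same samples gave 0.694–0.708. A cruder iterative re-estimate in 90 of the Step 4 patients, in the table's row order, gave 0.69, 0.73 and 0.77 against realised ratios of 0.68, 0.68 and 0.74. Most of the bias is removed, though not all of it with the crude method.

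**The case against.** The strongest reply is that Section 6.6 never says the interaction will be judged by averaging post hoc clearances. Section 3.3.8 speaks of comparing PK data, which can include observed concentrations against model predictions. Table 1 makes concentrations the endpoint, and Cmax and Cmin are to be summarised by study day. None of these is shrunk, and the Day 15 trough would show a shift of the simulated size. This stands: a reader might infer that the assessment rests on post hoc clearance alone, and the documents do not support that.

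Four further limits also stand.
- **The prior.** The existing model is not described. Study GP28363 (Section 1.3.5.1) collected PK on the combination, and whether those data entered the model cannot be seen. That the typical value means no interaction is an inference from Section 3.3.8.
- **The size.** A reader might infer that a real interaction will be understated materially, or missed. With large between-patient variability and small residual error the loss is negligible. Any rate of missed interactions needs an equivalence range that the protocol does not set. Shrinkage also need not cost test power: power on post hoc values was 1.00 in every non-null scenario of a 25-trial run.
- **Atezolizumab.** A reader might extend the point to it. It has up to 10 samples per patient and a concurrent Cohort C comparison, and no attenuation was shown for it.
- **Exposure-response.** A reader might infer that these analyses inherit the shrunken values. Section 6.6 says only drug exposure, and Table 1 names concentrations.

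On the remedy, a combination effect estimated against historical data is confounded with study, population and assay differences. That is true, but it applies equally to a post hoc comparison with the same data. The clause on additional PK analyses permits the remedy without committing to it.

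**Conclusion.** The point holds for cobimetinib, worded as a risk. The only model-based method that Section 6.6 states would, if its estimates are averaged to judge the interaction, lean toward no interaction. The loss runs from about 4% of the log effect (1 − 0.96) to more than half (1 − 0.42 = 58% in the linearised calculation, 1 − 0.33 = 67% in the worst nonlinear check). A true ratio of 0.70 could appear as about 0.71–0.89, so a 43% rise in exposure would read as between 1/0.89 − 1 = 12% and 1/0.71 − 1 = 41%. These figures rest on the assumed variability, half-life and one-compartment structure, and on a single-agent prior. The documents fix none of them. Unshrunk observed data are also planned, but no rule says how they enter the interaction judgement or what happens if they disagree with the post hoc clearances. This is a worthwhile, cheap improvement to a descriptive analysis. It changes no test and no sample size.

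**What to change.** In Section 6.6, for cobimetinib:
- Judge the interaction by estimating combination treatment as a fixed effect on CL/F. Fit by likelihood, either pooled with single-agent data or with the other model parameters fixed, and report the clearance ratio with a 90% CI.
- Show observed Cohort A Day 15 Cmin and 2–4 h concentrations against single-agent data or model predictions.
- Report eta-shrinkage with any post hoc values, and do not average those values to judge the interaction.

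For atezolizumab the same model is optional.

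The cost is a short addition to the text and one extra model fit on samples already scheduled. The interval may be wide. The ratio will remain confounded with between-study differences, because cobimetinib has no concurrent single-agent cohort; the report should say so.
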